5.9.2 Secondary study parameters/endpoints (if applicable)

n.a.

5.9.3 Other study parameters (if applicable)

n.a.

5.10 Randomisation, blinding and treatment allocation

n.a.

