2. STUDY POPULATION

2.1 Population (base)

2.2 Inclusion criteria

In order to be eligible to participate in this study, a subject must meet all of the following criteria:

-10 healthy volunteers

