2.4 Sample size calculation

AFI of the fingertip is a completely new application, there are no data on the basis of which a sample-size calculation can be done. It is a pilot study. The results of this pilot will serve to calculate a sample size for a follow-up study.

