5.9 Study parameters/endpoints

5.9.1 Main study parameter/endpoint

- magnitude and time course of the flavoprotein response
- linearity of the electrical stimulation with the flavoprotein response
- block of the flavoprotein response by lidocaine / prilocaine cream and 8% capsaicin patches

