5.11 Study procedures

- 1) Each subject will undergo a series of electrical stimuli (5Hz, for 10 seconds) with AFI measurement. Each stimulus strength (0.5, 0.6, 0.7, 0.8, 0.9 and 1.0 mA) will be administered twice. The stimulus is interrupted when the pain intensity exceeds 7. Thereafter, a (non-painful) 2000Hz, 1.0mA stimulus will be administered as a (negative) control for 10 seconds. The stimuli are administered by a Neurometer, a validated before (11). The middle finger is illuminated with a white light source, from which blue light with a wavelength of 480nm is filtered. This light excites oxidized flavoproteins. The signal is picked up by a digital camera that is connected to an upright microsoop. The stimulation and measurements take 15 minutes.

- 2) At the end of the above measurements, the middle finger tip is smeared with lidocaine / prilocaine cream. An hour later the test person returns for the same measurements described above (15 minutes).
- 3) At the end of the measurements described under 2) an 8% capsaicin patch is applied to the middle finger tip. After an hour the researcher comes along and the plaster is removed. A week later the test person returns to undergo the measurements as described under 1) again (15 minutes).

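### Section 5.10 declares blinding not applicable, although the camera recordings could be read without knowledge of stimulus strength, frequency or session

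*Protocol*

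**What the plan says.** Protocol section 5.10 treats three subjects under one heading, "Randomisation, blinding and treatment allocation", and its whole content is n.a. No other section provides for masked or independent reading. Section 9.1 codes subjects by number in order of entry, which conceals neither the stimulus nor the session.

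On measurement, section 5.11 says: "The signal is picked up by a digital camera that is connected to an upright microsoop". It does not say how an amplitude is obtained from the recording, or by whom.

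The main parameters in section 5.9.1 include "magnitude and time course of the flavoprotein response", linearity with the stimulus, and "block of the flavoprotein response by lidocaine / prilocaine cream and 8% capsaicin patches". Section 7.1 analyses strength by correlation and linear regression. It compares baseline with the cream session and with the patch session by repeated-measures ANOVA, and 5 Hz with 2000 Hz at 1.0 mA by a paired t-test.

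**The concern.** Blinding of the person stimulated and blinding of the person who reads the recording are separate questions. The first is hardly feasible here: the subject feels the current, and the operator sets it. The second is feasible, because a camera separates the reading from the stimulation. A bare n.a. dismisses both.

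This matters because the favourable result of the main comparisons is known in advance. Amplitude should rise with current, fall after cream and after patch (both described as negative controls in section 3.2), and be small for the 2000 Hz negative control. If a person who knows the condition exercises any judgement in extracting amplitude, errors can lean in that direction. The pilot is meant to show that the signal is reproducible and valid, and section 2.4 says its results will size a follow-up study. A reading bias would thus affect both the validity claim and the effect estimate carried forward.

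**Working it through.** **Is masked reading provided anywhere?** Setting the relevant sections side by side:

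- 5.10: n.a. for randomisation, blinding and allocation together.
- 5.11: camera capture is described; extraction is not.
- 7.1: amplitudes are analysed by strength, session and frequency; nothing is said about the reader.
- 9.1: subjects are coded, recordings are not.

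Neither masked reading nor fixed automated extraction is stated.

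**How many recordings would need coding?**

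- Section 5.11: "Each stimulus strength (0.5, 0.6, 0.7, 0.8, 0.9 and 1.0 mA) will be administered twice", so 6 × 2 = 12 recordings at 5 Hz.
- Section 5.11 also says: "Thereafter, a (non-painful) 2000Hz, 1.0mA stimulus will be administered as a (negative) control for 10 seconds". That adds 1, giving 12 + 1 = 13 per session.
- There are three sessions (baseline, after cream, one week after patch): 13 × 3 = 39 per subject.
- Section 2.2: "10 healthy volunteers", so 39 × 10 = 390 in total.

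This assumes that the full series is repeated at each session. It excludes any recordings made with other filter settings, for which section 5.11 gives no number.

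**What could a reading bias do?** The protocol has no figure to reproduce. Section 2.4 states that "there are no data on the basis of which a sample-size calculation can be done", and no significance level, SD or effect size is given. What follows is therefore an illustration only.

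- Test: the paired t-test of section 7.1 (5 Hz versus 2000 Hz), n = 10, df = 10 − 1 = 9.
- Assumed level: two-sided 5%.
- Assumed bias: with no true difference, knowing the condition shifts the mean extracted difference by b, in units of the SD of the within-subject differences.
- Under that bias the test statistic follows a noncentral t distribution with noncentrality b × √10. The false-positive rate is the probability that its absolute value exceeds the usual 5% critical value.

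| b (SD) | b × √10 | False-positive rate |
|---|---|---|
| 0 | 0 | 5.0% |
| 0.1 | 0.32 | 5.9% |
| 0.2 | 0.63 | 8.8% |
| 0.3 | 0.95 | 13.6% |
| 0.5 | 1.58 | 29.3% |

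The documents give no basis for choosing a row. The table does not carry over to the regression on strength or to the repeated-measures ANOVAs, which have different error structures. Fully effective masking corresponds to b = 0 and keeps the assumed 5%.

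**The case against.** The strongest reply is that n.a. was entered under a template heading in a single-group study in which every subject follows the same sequence. It may mean only that there are no arms to allocate or mask. It does not say that recordings will be read with knowledge of the condition, and a reader who infers that goes beyond the text. This stands as a limit on the charge. It does not make the entry adequate: blinding belongs in that section, the entry dismisses it, and nothing elsewhere restores it.

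A reader might also infer that an analyst will choose regions and frames by hand and discard recordings at will. The protocol says none of this. If extraction is automated and fixed, the mechanism largely disappears. Details such as region of interest, analysis window and rejection rules are commonly left to an SAP or an imaging manual, so their absence is not counted here. What remains is that section 5.10 gives neither safeguard.

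It would likewise be tempting to say that every main endpoint is affected in a known direction, or that the plan has an error rate of 9–29%. Neither is supported. No direction is stated for the time course, and the 2000 Hz contrast is not listed among the main parameters in section 5.9.1. The 9–29% range depends on an unanchored shift of 0.2–0.5 SD and leaves out smaller ones.

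Finally, masking may leak. Section 5.4 lists paleness, redness and oedema after the cream and redness after the patch, any of which might show on the imaged skin. Section 5.11 interrupts a stimulus when pain exceeds 7, which could reveal a high current. An analyst who also made the recordings may remember them. These points limit the benefit of coding but do not remove it.

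**Conclusion.** The point holds as a design weakness that can be corrected: blinding is declared not applicable, although masked reading of the recordings is feasible and nothing in the protocol takes its place. The strength, block and 5 Hz versus 2000 Hz comparisons are exposed to expectation bias to the extent that extraction involves human judgement, which the protocol leaves open. The bias is a risk and has not been shown to occur, and its size cannot be derived from the documents. The tabulated rates apply only to the paired t-test, under an assumed two-sided 5% level and assumed shifts. Pilot status does not remove the point, since the results are to inform the next study. Nor does masked reading resolve the fixed order of sessions, which is a separate matter.

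**What to change.** Replace n.a. for blinding in section 5.10 with a statement along these lines:

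> Subjects and the operator are not blinded. Recordings are given random codes, and amplitudes are extracted and locked before the codes for strength, frequency and session are opened; or amplitudes are extracted by a prespecified automated algorithm applied identically to all recordings.

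Randomisation and allocation can stay n.a. Technical settings for the extraction can be left to the SAP or an imaging manual.

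The cost is renaming about 390 files and keeping the code list away from the reading until amplitudes are locked. No additional subject or visit is needed, and coding does not in itself require a second reader. If the analyst also made the recordings, a reader without the code or the automated route gives better protection against recall. The report should acknowledge that masking may be incomplete for recordings with visible skin changes or interrupted stimuli.

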5.11 Study procedures

- 1) Each subject will undergo a series of electrical stimuli (5Hz, for 10 seconds) with AFI measurement. Each stimulus strength (0.5, 0.6, 0.7, 0.8, 0.9 and 1.0 mA) will be administered twice. The stimulus is interrupted when the pain intensity exceeds 7. Thereafter, a (non-painful) 2000Hz, 1.0mA stimulus will be administered as a (negative) control for 10 seconds. The stimuli are administered by a Neurometer, a validated before (11). The middle finger is illuminated with a white light source, from which blue light with a wavelength of 480nm is filtered. This light excites oxidized flavoproteins. The signal is picked up by a digital camera that is connected to an upright microsoop. The stimulation and measurements take 15 minutes.

- 2) At the end of the above measurements, the middle finger tip is smeared with lidocaine / prilocaine cream. An hour later the test person returns for the same measurements described above (15 minutes).
- 3) At the end of the measurements described under 2) an 8% capsaicin patch is applied to the middle finger tip. After an hour the researcher comes along and the plaster is removed. A week later the test person returns to undergo the measurements as described under 1) again (15 minutes).

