Figure 2: high density of nociceptor endings in the epidermis, demonstrated by immunohistochemical staining with PGP9.5. The endings have a somewhat "variceus" aspect. In these thickenings there is a high concentration of mitochondria (see figure 3).

Figure 3: electron microscopic recording of an axon terminal (A) and Schwann cell (SC) of a nociceptor termination. The arrow shows 11 mitochondria in this ending.

Figure 4: sharp decrease in the number of epidermal nociceptor endings in an animal model for neuropathy. sham = control animal, CCI = animal with chronic constriction injury (model

for neuropathy), u.dermis is upper dermis. The arrowheads show PGP9.5 labeled epidermal nociceptor endings, which are completely absent in the epidermis in the animal with neuropathy.

OBJECTIVES

Primary Objective:

To study whether painful neuropathy can be measured with flavoprotein imaging, first of all a pilot study is needed, with which we want to investigate whether a reproducible and validated flavoprotein signal can be obtained at the second fingertip of healthy subjects.

STUDY DESIGN

- studying whether there is a time relationship between administering an electrical stimulus by means of finger electrodes and an optical (flavoprotein) signal on the fingertip of test subjects
- studying whether there is a linear relationship between the strength of the applied electrical signal and the size of the optical (flavoprotein) signal
- studying whether the signal is specific to the flavoprotein wavelength, by changing the filter settings of the camera
- studying whether the optical (flavoprotein) signal can be blocked by administering lidocaine / prilocaine cream on the fingertip
- studying whether the optical (flavoprotein) signal can be blocked by administering a capsaicin 8% patch on the fingertip.

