7. STATISTICAL ANALYSIS

7.1 Primary study parameter(s)

-corelation coefficients between stimulus strength and AFI signal amplitude will be calculated. The statistical significance of the correlation will be calculated using linear regression analysis.

-repeated-measures ANOVAs will be performed between baseline recordings and recordings 1 hour after application of lidocaine/prilocaine cream and between baseline recordings and recordings 1 week after application of a capsaicin patch. Finally, a paired t-test will be used to compare 1.0mA, 5Hz and 1.0mA, 2000Hz electrical stimulation.

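### Over the twofold current range planned (0.5 to 1.0 mA), a good straight-line fit is weak evidence of linearity, and the endpoint does not limit its claim to that range

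*Protocol*

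**What the plan says.** Under Study Design, one aim is "studying whether there is a linear relationship between the strength of the applied electrical signal and the size of the optical (flavoprotein) signal". Section 5.9.1 carries this into the main endpoints as "linearity of the electrical stimulation with the flavoprotein response". Neither place names the currents over which linearity is to be shown.

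Section 5.11 fixes the levels: "Each stimulus strength (0.5, 0.6, 0.7, 0.8, 0.9 and 1.0 mA) will be administered twice". The lowest 5 Hz level is therefore half of the highest. The same section adds that "The stimulus is interrupted when the pain intensity exceeds 7", which may remove recordings at the upper end in some subjects.

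The planned analysis in 7.1 is that "corelation coefficients between stimulus strength and AFI signal amplitude will be calculated" and that "The statistical significance of the correlation will be calculated using linear regression analysis". The sample is "10 healthy volunteers" (2.2). Section 2.4 states that "there are no data on the basis of which a sample-size calculation can be done", so no size is given for the signal or the noise.

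**The concern.** A correlation and a slope p-value show that the response rises with current. They do not show that it rises in a straight line. That distinction matters most when the levels are close together, because a short stretch of a curve looks straight. Here all six levels lie between half the maximum and the maximum.

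The risk is that the pilot reports a linear stimulus-response relation from a high correlation when a square-root, logarithmic, saturating or quadratic response would have given almost the same result. A later study could then rely on proportionality at currents that were never recorded. Replacing the slope test with a curvature test is right in principle, but the range limits how much such a test can learn about mild curvature.

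**Working it through.** The plan has no power figure or noise estimate to reproduce, so the calculation is conditional on assumptions.

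**Inputs from the protocol:** six equally spaced levels, 0.5 to 1.0 mA, two runs each (5.11); 10 subjects (2.2). The ratio of highest to lowest level is 1.0/0.5 = 2.

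**Assumptions:** the response shape; run-to-run SD, as a share of the 1.0 mA response; two-sided 5% level; no true difference in curvature between subjects (any such difference would lower power).

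**Step 1. Fit without noise.** Each curve is scaled to 1 at 1.0 mA and a least-squares line is fitted through the six levels. For the square root the values are 0.707, 0.775, 0.837, 0.894, 0.949 and 1.000.

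**Step 2. Curvature contrast.** For six equally spaced levels the quadratic contrast is L = (5y₁ − y₂ − 4y₃ − 4y₄ − y₅ + 5y₆)/√84.

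| Shape | R² of line | Rise, 0.5 to 1.0 mA | Size of L |
|---|---|---|---|
| √x | 0.998 | 0.29 | 0.0122 |
| log(1+5x) | 0.994 | 0.30 | 0.0196 |
| x/(x+0.5) | 0.986 | 0.25 | 0.0245 |
| x² | 0.991 | 0.75 | 0.0611 |

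The largest departure from the line is between 0.7% (√x) and 3.3% (x²) of the 1.0 mA response.

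**Step 3. Power of a curvature test.** This is a one-sample t-test on the 10 per-subject contrasts (9 df), with noncentrality L/(SD/√(10 × 2)). Example, √x at SD 0.20: 0.0122/(0.20/4.472) = 0.27, power 6%. Example, x² at SD 0.10: 0.0611/(0.10/4.472) = 2.73, power 68%.

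| Run SD | √x | log(1+5x) | x/(x+0.5) | x² |
|---|---|---|---|---|
| 2% | 68% | 97% | >99% | >99% |
| 5% | 17% | 35% | 50% | >99% |
| 10% | 8% | 12% | 17% | 68% |
| 20% | 6% | 7% | 8% | 23% |
| 30% | 5% | 6% | 6% | 13% |

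**Step 4. What a confidence interval would show.** The 95% half-width for L is 2.262 × SD/√20. The fitted quadratic's departure from the line at the two end levels is 5/√84 = 0.546 times L. At SD 20% the half-width in that departure is 0.546 × 2.262 × 0.20/4.472 = 5.5% of the 1.0 mA response. At 10% it is 2.8%, and at 5% it is 1.4%.

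**Step 5. The planned slope test.** For a straight rise of 1 over the range, the linear contrast is 2 × √0.175 = 0.837. Even if the SD equals the whole rise, the noncentrality is 0.837 × 4.472/1 = 3.74 and power is 96% (108 df: 120 readings less 10 subject effects, slope and quadratic term). A significant slope is therefore likely for almost any rising response.

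**Step 6. Abrupt shapes.** A plateau from 0.8 mA or a threshold at 0.7 mA gives a line R² of 0.864, and a plateau from 0.7 mA gives 0.690. With SD equal to half of the rise, the quadratic test finds the plateau from 0.8 mA with 83% power on 108 df (74% on 9 df).

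**Step 7. Loss at the top.** Take SD as 0.1 of the full-range rise, on the pooled df (108 for the full range). If levels above 0.8 mA were lost in every subject, power would fall from 46% to 11% (√x), from 96% to 34% (log x) and from 95% to 22% (x²). This is an extreme case, because 5.11 does not say how often interruption is expected.

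**The case against.** A reader might infer that the linearity endpoint cannot be answered at all, even with a correct curvature test. The documents do not support that, for three reasons.

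- **Noise is unknown.** At a run SD of 2%, power against the same four curves is 68% to over 99%. The 20% case is severe for the concave shapes: their rise is only 0.25 to 0.30 of the 1.0 mA response, so that SD is about 66% to 80% of the rise. On the other hand, an SD of one tenth of that rise means single-run precision of about 2.5% to 3%, and nothing in the protocol shows that this is attainable.
- **Not every curve is hidden.** Saturation or a threshold inside the range would show (Step 6).
- **No wider claim is made explicitly.** The aim concerns the applied signal, and 5.11 defines what is applied. A departure of at most 3.3% is close to linear over those currents, which is itself an answer.

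A reader might also infer that the levels must be moved. That does not follow. The Introduction bases the method on nociceptive stimulation, and the protocol does not say whether weaker currents would qualify. Spreading the same trains evenly down to 0.2 or 0.1 mA, as a pure illustration, would lower the mean amplitude available for the cream and patch comparisons by about 13% to 33% for these four shapes. The currents given to volunteers are for the investigator to decide.

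These objections remove the stronger readings. They leave standing that the endpoint has no stated range and that the analysis in 7.1 does not examine shape.

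**Conclusion.** The concern holds in a limited form. Over 0.5 to 1.0 mA, mild smooth curves are nearly indistinguishable from a line (R² about 0.99). A high correlation or significant slope is therefore weak evidence of linearity. A curvature test has low power against such curves unless run-to-run noise is small, roughly below 5% of the 1.0 mA response for the concave shapes.

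The R² values follow from the planned levels and the assumed shapes. The power figures also rest on the assumed SD and on equal curvature across subjects. The recordings can support a statement about approximate linearity within the tested currents, with a precision that the confidence interval would make visible (Step 4). They cannot support a statement about currents below 0.5 mA.

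**What to change.** Keep the stimulus levels in 5.11, and change the wording in three places:

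- **Study Design and 5.9.1:** restrict the linearity aim and endpoint to approximate linearity between 0.5 and 1.0 mA.
- **7.1, analysis:** add a within-subject quadratic (curvature) term, reported as an estimate with its 95% confidence interval.
- **7.1, interpretation:** state that linearity will not be concluded from the correlation or the slope p-value alone, and that a non-significant curvature term will be read together with its interval.

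This needs no extra trains, visits or subjects. The cost is a narrower claim and one more estimate to report. The interval may turn out wide, but that is useful information for the follow-up study. Any change in the stimulus range is for the investigator and is not proposed here.

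### The 2000 Hz control always comes last and the order of the 5 Hz strengths is not stated, so the planned paired t-test cannot tell frequency specificity from a signal that falls within the session

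*Protocol*

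**What the plan says.** Protocol section 5.11 sets the measurement series. For the 5 Hz stimuli, "Each stimulus strength (0.5, 0.6, 0.7, 0.8, 0.9 and 1.0 mA) will be administered twice", which makes twelve runs. The order of the strengths is not given; they are only listed from low to high. A safety rule applies: "The stimulus is interrupted when the pain intensity exceeds 7". The control follows: "Thereafter, a (non-painful) 2000Hz, 1.0mA stimulus will be administered as a (negative) control for 10 seconds". On timing, "The stimulation and measurements take 15 minutes". The same series is repeated an hour after the cream and a week after the capsaicin patch, each time on the middle fingertip that received the product. Section 5.10 marks randomisation and blinding as not applicable.

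Section 7.1 states that "a paired t-test will be used to compare 1.0mA, 5Hz and 1.0mA, 2000Hz electrical stimulation". For the cream, "repeated-measures ANOVAs will be performed between baseline recordings and recordings 1 hour after application of lidocaine/prilocaine cream", with a matching comparison of baseline and one week for capsaicin. Section 5.9.1 lists linearity of the response with stimulus strength among the main endpoints, and also "block of the flavoprotein response by lidocaine / prilocaine cream and 8% capsaicin patches". No untreated finger, vehicle or untreated repeat session is described.

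**The concern.** In every session the control is the thirteenth run and every 5 Hz run precedes it. If the optical signal declines over a session for any reason, the control reads lower than the 1.0 mA, 5 Hz runs even when frequency makes no difference. The planned paired t-test would count that as a frequency effect. A rising signal would work the other way and hide a true effect.

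The unstated order of the strengths matters twice. It fixes how far the control lies from the 1.0 mA runs, and it decides whether strength is tied to run position, which affects the linearity endpoint.

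The pilot is meant to show that the signal is reproducible and valid, and section 2.4 says that its results will be used to size a follow-up study. Section 2.4 also calls the fingertip application completely new and without data, so a stable signal cannot be taken for granted. The other planned check, "studying whether the signal is specific to the flavoprotein wavelength, by changing the filter settings of the camera", concerns wavelength and says nothing about drift over time.

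**Working it through.** The protocol states no figure to reproduce: there is no alpha, SD, effect size or drift estimate.

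**Inputs.** From the protocol: 6 strengths × 2 = 12 runs at 5 Hz, control as run 13, 10 subjects, paired t-test. Assumed: two-sided 5% level; the contrast is the mean of the two 1.0 mA, 5 Hz runs minus the 2000 Hz run (section 7.1 does not say); no true frequency effect; a linear fall of *d* SDs of the paired difference per run.

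**Formulas.** Gap *g* = position of the control − mean position of the two 1.0 mA runs. Shift δ = *d* × *g*. The false-claim rate is the two-sided rejection probability of a noncentral t with 9 df and noncentrality δ√10.

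| Order | 1.0 mA runs | Control | *g* | Rate, *d* = 0.05 | Rate, *d* = 0.1 | Strength-position correlation |
|---|---|---|---|---|---|---|
| Ascending pairs | 11, 12 | 13 | 13 − 11.5 = 1.5 | 5.5% | 7.1% | 0.99 |
| Two ascending sweeps | 6, 12 | 13 | 13 − 9 = 4.0 | 8.8% | 20.5% | 0.49 |
| Descending pairs | 1, 2 | 13 | 13 − 1.5 = 11.5 | 36.9% | 89.8% | −0.99 |
| Up, control, down (proposed) | 6, 8 | 7 | 7 − 7 = 0 | 5.0% | 5.0% | 0 |

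**Slope (linearity), linear drift of 0.1 SD per run.**
- Ascending pairs: mean position moves from 1.5 at 0.5 mA to 11.5 at 1.0 mA, so the bias across the range is −0.1 × 10 = −1.0 SD.
- Two ascending sweeps: mean position moves from 4 to 9, so the bias is −0.1 × 5 = −0.5 SD.
- Proposed order: the *i*-th strength is at positions *i* and 14 − *i*, mean 7 for all, so the bias is 0.

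**Slope, early non-linear drift** (exponential, total 1.2 SD over the 13 runs).
- Time constants of 1 to 10 runs: −0.64 to −1.03 SD for ascending pairs, −0.52 to −0.17 SD for the proposed order.
- Against two ascending sweeps: −0.52 SD for both at a time constant of 1 run; −0.56 SD (sweeps) against −0.51 SD (proposed) at 2 runs.

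**Control contrast, same early drift, time constants 1 to 6 runs.** Ascending pairs 5.0-5.3%, two sweeps 5.0-9.8%, proposed 5.0%.

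**Can analysis separate order from frequency?** A model with six strength terms, a 2000 Hz term and a linear position term has full rank for all these orders, because each strength is repeated. Adjustment raises the SD of the 5 Hz minus 2000 Hz contrast by 22% (ascending pairs), 5% (two sweeps) or 5.5-fold (descending pairs). The protocol describes no such model.

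**Block.** With no true block, a fall between sessions of 0.5 or 1.0 SD of the paired difference gives significance in 29% or 80% of trials. This is simply the behaviour of a paired t-test at n = 10 under an assumed shift. Fade within a session that is the same in every session cancels from this comparison.

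**The case against.** The strongest reply is that the natural reading of section 5.11 does little harm to the frequency contrast. Strengths are listed low to high. If they ascend in pairs, the two 1.0 mA runs come just before the control and the error rate stays near 5-7% under linear or early drift. A fade of 1% or 5% per run would then lower the 2000 Hz response by only 1.5% or 7.4%, far from the absent response that a negative control should show. Frequency specificity is also not a listed main endpoint, the trial is an open pilot in 10 volunteers, and nothing shows that drift occurs. All of that stands and limits the weight of the point. It does not remove it: the order is not fixed, and ascending pairs pass the problem to linearity, which is a main endpoint.

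Four stronger readings are not supported:
- A reader might infer that no analysis can ever separate frequency from run order. The repeated strengths allow a position-adjusted model, although it depends on the shape of the drift.
- A reader might take the 90% rate as the expected error. It belongs to descending pairs, which the text does not suggest.
- A reader might conclude that the block result is shown to be biased. It is only uncontrolled. Two agents are tested at two intervals, one hour and one week, and a single drift explanation would have to fit both.
- A reader might fault the cream-then-capsaicin sequence. Section 10.1 gives a reason for it.

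The Summary places numbness on the index fingertip whereas section 5.11 puts both products on the middle fingertip. These need reconciling, but neither version supplies an untreated recording site.

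**Conclusion.** The point holds in a limited form. By procedure the control is always last, and the planned unadjusted paired t-test cannot distinguish a frequency effect from a fall in signal during the session. Under an assumed linear drift of 0.1 SD per run the false-claim rate is about 7% (ascending pairs) or 20% (two ascending sweeps), against a nominal 5%. Under ascending pairs the more serious effect is on linearity, where strength and run position are almost the same variable. Every size rests on assumed drift; the documents neither show nor exclude it.

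The before-after measurement of block is a separate limit on interpretation. Minor to moderate for an exploratory pilot, and worth acting on because the repair is cheap.

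**What to change.** In section 5.11, state that the same twelve 5 Hz runs are given as one ascending then one descending series, with the 2000 Hz run between the two 1.0 mA runs (run 7 of 13), identically in all three sessions and with the existing pain-interruption rule unchanged. This adds no stimuli, subjects, visits or time: still 13 runs in 15 minutes (900 s / 13 = 69 s per run on average). The planned tests stay as they are.

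Limits and downsides:
- Linear-drift bias goes from both contrasts. Under early non-linear drift some slope bias remains, with little or no gain over two ascending sweeps when the drift is very early.
- The two strongest runs lie close together, separated only by the 2000 Hz run.
- If one 1.0 mA run is lost to the pain rule, the gap becomes one run. If that happened in every subject, the error rate at 0.1 SD per run would be 5.9%.

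If the study team finds this order unacceptable, section 5.11 should state the order used, and section 7.1 should add a run-position term to the 5 Hz versus 2000 Hz and slope analyses.

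Separately, report block as an uncontrolled before-after change that cannot be attributed to the product alone. That is one sentence. It makes the limit plain but does not remove it.
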